#### **8.2.6. Absence of MBS Postdose**

The proportion of subjects with their Screening MBS among nausea, photophobia and phonophobia absent at 15, 30, and 45 minutes and 1, 1.5, 2 (DB2 period), 4, and 24 hours postdose during each DB treatment period will be summarized by treatment group and time point for the FAS1 and FAS2. The corresponding p-values from Fisher's exact test will be computed for the comparison between treatment groups. Subjects who report an MBS at Screening among nausea, photophobia and phonophobia (those with only one of the three symptoms reported will have that symptom designated as MBS by default), and have this symptom present at predose and report the status of their symptoms at the particular postdose time point will be analyzed.

Absence of Screening MBS will be analyzed similarly at all postdose timepoints for both treatment periods.

#### **8.2.7. Change in Functional Disability Score Postdose**

The values of the functional disability scale are: 0 = no disability, able to function normally; 1 = performance of daily activities mildly impaired, can still do everything but with difficulty; 2 = performance of daily activities moderately impaired, unable to do some things; 3 = performance of daily activities severely impaired, cannot do all or most things, bed rest may be necessary.

The change in functional disability score from baseline to 2, 4, and 24 hours postdose during each DB treatment period will be summarized by treatment group for the FAS1 and FAS2. The corresponding p-values from the Wilcoxon rank-sum test will be computed for the comparison between treatment groups. P-values from the Wilcoxon signed-rank test will be computed for the change from baseline within each treatment group.

The following levels of change from baseline in functional disability score will be compared between DFN-15 and placebo in each DB period: 3 point change, 2 point change, 1 point change, 0 point change, -1 point change, -2 point change, and -3 point change. The proportion of subjects with those levels of change from baseline during each DB treatment period will be summarized by treatment group and time point for the FAS1 and FAS2. The corresponding p-values from Fisher's exact test will be computed for the comparison between treatment groups for each category.

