#### **9.2.1.4.1 Efficacy Assessments**

Subjects will be provided with an eDiary at screening (V1) to collect at least 1 migraine attack during the screening period. The migraine episode may be treated with medication the subject currently uses for a migraine during this period, unless otherwise instructed by the Investigator. After at least 1 migraine attack has been recorded in the eDiary, as instructed, the subject will contact the study site to schedule Visit 2 (V2). At V2 (randomization), it will be determined if subjects meet all study requirements and are eligible to continue in the study. If a subject does not meet all requirements, they must return all study equipment that was provided at the Screening Visit. If randomized, subjects will continue to collect migraine data (for a migraine attack treated with study drug), study drug, last food intake and fat content, and any rescue medication used to treat a migraine. Subjects will record migraine predose assessments, study drug date and time taken, and postdose efficacy data in real time in the 2 DB periods through V4/ET:

- Level of headache pain at predose and at various time points postdose (Levels: 0 = none; 1 = mild; 2 = moderate; 3 = severe)
- Time to meaningful pain relief (based on subject's perception) and time to pain-freedom after study drug
- Migraine symptoms and MBS other than pain: nausea, photophobia, and phonophobia at predose and at various time points postdose; allodynia
- Functional disability at predose and at various time points postdose; scale: 0 = no disability, able to function normally; 1 = performance of daily activities mildly impaired, can still do everything but with difficulty; 2 = performance of daily activities moderately impaired, unable to do some things; 3 = performance of daily activities severely impaired, cannot do all or most things, bed rest may be necessary
- Treatment satisfaction (7-point scale)
- PPMQ-R

MBS will also be collected during Screening via Migraine History evaluation and this Screening MBS will be used for the evaluation of the second co-primary endpoint.

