##### ***10.4.2 Secondary Endpoints:***

- The proportion of subjects with TEAEs after study drug compared between DFN-15 and placebo.
- The proportion of subjects who are free from nausea, photophobia, and phonophobia at 15, 30, and 45 minutes and 1, 1.5, 2, 4, and 24 hours postdose compared between DFN-15 and placebo in each DB period.
- Time to meaningful pain relief (defined as based on subject's perception) within 2 hours postdose compared between DFN-15 and placebo in each treated attack in each DB period.

- Time to pain freedom within 2 hours postdose compared between DFN-15 and placebo in each DB period.
- The proportion of subjects who have pain relief at 15, 30, and 45 minutes and 1, 1.5, 2, 4, and 24 hours postdose compared between DFN-15 and placebo in each DB period.  
Headache pain relief is defined for DB1 as a reduction from moderate or severe pain prior to dosing reduced to mild or none postdose, and for DB2 as moderate or severe pain predose reduced to mild or none postdose, or mild pain predose reduced to none postdose
- The proportion of subjects who are pain-free at 15, 30, and 45 minutes and 1, 1.5, 2 (DB2 period), 4, and 24 hours postdose compared between DFN-15 and placebo in each DB period.
- The proportion of subjects with their Screening MBS (and have this symptom predose) absent at 15, 30, and 45 minutes, and 1, 1.5, 2 (DB2 period), 4, and 24 hours postdose compared between DFN-15 and placebo in each DB period.
- Change in functional disability score at 2, 4, and 24 hours postdose compared between DFN-15 and placebo in each DB period.
- Among those reporting cutaneous allodynia predose, the proportion of subjects who are pain-free at 2 and 4 hours postdose compared between DFN-15 and placebo in each DB period.
- The proportion of subjects who are pain-free at 2 and 4 hours postdose whose BMI is < 30 vs. subjects whose BMI is ≥ 30, and whose BMI is < 25 vs. subjects whose BMI is ≥ 25 in each DB period.
- The proportion of subjects who have pain recurrence between 2 to 24 hours (i.e., pain-free at 2 hours postdose, with pain [mild, moderate, or severe] reported at 24 hours postdose) compared between DFN-15 and placebo in each DB period.
- The proportion of subjects who have sustained pain relief at 2 to 24 hours postdose (i.e., pain-relief at 2 hours postdose, with no use of rescue medication and no recurrence of headache pain within 2 to 24 hours postdose) compared between DFN-15 and placebo in each DB period.

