## 6.2. KEY DEFINITIONS

### 6.2.1. Baseline

Unless specified otherwise, the baseline assessment will be the latest available valid measurement taken prior to the administration of the initial dose of study drug during each DB period. In the event that a migraine attack happens immediately following randomization, the assessments taken on the same day as the administration of the initial dose of study drug, but prior to the time study drug is taken, can be considered as baseline.

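### Functional disability is compared between arms by an unstratified rank-sum test on raw change; stratifying by the collected predose grade would cost almost nothing and could add power

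*SAP*

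**What the plan says.** Protocol 10.4.2 lists the secondary endpoint as "Change in functional disability score at 2, 4, and 24 hours postdose compared between DFN-15 and placebo in each DB period". Protocol 10.5.2 leaves the analysis of secondary endpoints to the SAP.

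SAP 8.2.7 defines a four-level scale ("The values of the functional disability scale are: 0 = no disability, able to function normally", up to 3 for severe impairment) and takes as its variable "The change in functional disability score from baseline to 2, 4, and 24 hours postdose during each DB treatment period". For the between-arm test it states: "The corresponding p-values from the Wilcoxon rank-sum test will be computed for the comparison between treatment groups". It adds a signed-rank test within each arm and a Fisher test for each level of change from -3 to +3. It names no stratification, covariate or model. The only regression in the SAP is the logistic model for the co-primary subgroups in 8.4.

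The predose grade is available in both periods. Protocol 9.2.1.4.1 has subjects record "Functional disability at predose and at various time points postdose", and the eDiary tables in both documents (Protocol Table 9-2, SAP Table 2) show it. SAP 6.2.1 sets the reference value: "the baseline assessment will be the latest available valid measurement taken prior to the administration of the initial dose of study drug", separately for each period.

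SAP 8.2 removes subjects with mild or no predose pain from the DB1 secondary analyses, and only those with no predose pain from DB2. These restrictions are on pain, not on disability.

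**The concern.** A change score does use the predose grade, but it fixes the slope at 1 whatever the data show. Where the slope that best predicts the postdose grade is not 1, predose variability that could have been removed stays in the test statistic.

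The bounded scale compounds this. A subject starting at grade 1 can improve by at most 1, a subject at grade 3 by up to 3, and a subject at grade 0 not at all. When all changes are ranked together, complete recovery from 1 to 0 counts as a smaller improvement than partial recovery from 3 to 1. Comparing subjects within the same predose grade avoids this.

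What is at stake is power, and so the chance of missing a real effect on the trial's only direct rating of disability, tested at three time points in two periods.

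**Working it through.** **The plan's own figures.** Neither document gives power for this endpoint. The nearest stated figure is 88% for the first co-primary (17.6% vs 29.2%, 600 subjects, 15% dropout). Evaluable per arm: 600 × 0.85 / 2 = 255. Pooled two-proportion formula: (0.116 × √255 − 1.96 × √(2 × 0.234 × 0.766)) / √(0.176 × 0.824 + 0.292 × 0.708) = (1.852 − 1.174) / 0.593 = 1.14, which gives 87.4%. This agrees with 88%, so 255 per arm is a fair DB1 size. No DB2 size is given; 217 per arm is assumed (255 × 0.85 = 216.75, a second 15% loss).

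**Linear approximation.** Let k be predose SD divided by postdose SD, and ρ the correlation of the recorded scores. In units of the postdose variance, the change score has variance 1 + k² − 2ρk and the baseline-adjusted comparison 1 − ρ². The efficiency of change relative to adjustment is therefore RE = (1 − ρ²) / (1 + k² − 2ρk). With the adjusted analysis at 80% power, the change score has power Φ(2.802 × √RE − 1.960). Power lost, in points:

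| k | ρ = 0.3 | ρ = 0.5 | ρ = 0.7 |
|---|---|---|---|
| 1.0 | 18.3 | 12.1 | 6.7 |
| 0.9 | 14.0 | 8.0 | 3.0 |
| 0.8 | 10.1 | 4.6 | 0.8 |
| 0.6 | 3.8 | 0.5 | 0.8 |

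For example, k = 1 and ρ = 0.5 give RE = 0.75 / 1 = 0.75 and power 67.9%. The change score does worse than ignoring the predose value only when ρ < k/2; that threshold is 0.5 only if the two SDs are equal.

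**Ordinal simulation.** Assumed model: bivariate latent normal cut to 0-3 grades, placebo 2-hour grades 0/1/2/3 of 25/35/25/15% (SD 1.00), active arm shifted by a fraction of a latent SD. Power is for the planned rank-sum on change versus van Elteren stratified by predose grade, 2,500 runs; rows marked as gain only were run separately, and – means no figure is available.

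| Setting (predose grades 0/1/2/3) | latent ρ 0.3 | latent ρ 0.5 | latent ρ 0.7 |
|---|---|---|---|
| DB1, 5/25/45/25%, 255 per arm, shift 0.25 | 64 vs 78% | 74 vs 82% | 86 vs 90% |
| DB1, 2/13/55/30%, shift 0.25 | 68 vs 77% | 79 vs 83% | 87 vs 89% |
| DB1, 1/14/60/25%, shift 0.25 (gain only) | – | 2.7 points | 1.1 points |
| DB1, 5/25/45/25%, shift 0.35 (gain only) | – | 2.2 points | 0.6 points |
| DB2, 20/35/30/15%, 217 per arm, shift 0.25 | 53 vs 71% | 62 vs 76% | 79 vs 86% |

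- The largest gains in the table are 78 − 64 = 14 points in DB1 and 71 − 53 = 18 in DB2. A separate run of the DB2 setting gave 51 vs 70%, which is 19 points; Monte Carlo error is about 1 point per power.
- At latent ρ 0.85 and shift 0.35 both tests are near full power and the gain is about 0 in either period.
- Under the null at latent ρ 0.5, rejection rates were 4.9% and 5.1%.

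**Reading the correlation.** The simulated ρ is latent. In the first DB1 setting, latent 0.5 corresponds to about 0.43 between recorded grades, and latent 0.7 to about 0.61. The predose SD there is √(4.30 − 1.90²) = 0.83, so k is about 0.83. Putting k = 0.83 and ρ = 0.43 into the approximation gives RE = 0.815 / 0.975 = 0.836 and a loss of 7.4 points, in line with the simulated 82 − 74 = 8.

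**Limits.** The ranges are not bounds. At latent ρ 0.2, the first DB1 setting gave 59 vs 76% and the DB2 setting 47 vs 69%.

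**The case against.** The strongest reply is that the plan tests exactly what it defines: the endpoint is a change score and the test ranks change scores. The test is valid under randomization, the co-primaries do not depend on it, and no power is claimed for it. SAP 6.1.1 says only that secondary testing can be performed, and the sequential procedure in 8.1.1 covers the co-primaries alone. All of this stands, and it makes the change optional. It does not remove the efficiency gain.

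The gain may also be small. DB1 keeps only moderate or severe predose pain. If that narrows predose disability, or the effect is larger than 0.25 SD, the gain falls to a few points or less. That stands too.

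Four stronger readings are tempting, and the documents do not support them:

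- **The plan ignores the predose grade.** It does not; it uses it by subtraction.
- **The between-arm comparison is biased by where subjects started.** Under randomization, predose imbalance is chance noise, and simulated type I error is near 5%. Whether 3 to 1 should outrank 1 to 0 is a judgement about the scale, not an error.
- **A definite loss, such as 6-18 points, can be attributed to the plan.** In the closed form that span needs equal SDs, correlations of 0.3-0.7 and an adjusted analysis at exactly 80% power. None of these is in the documents.
- **This is the only secondary measure touching function.** The PPMQ-R has a four-question function subscale (SAP 8.2.15), although it measures satisfaction rather than disability.

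**Conclusion.** The point holds as an efficiency matter on one secondary endpoint. The planned rank-sum test is valid but generally less efficient than a test conditioning on the predose grade. Van Elteren matched or beat it, within Monte Carlo error, in every setting simulated.

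The gain is roughly 0-14 points in DB1 and, if predose grades spread more widely there, roughly 0-18 points in DB2. These ranges rest on a latent-normal model, a shift of 0.25-0.35 SD, latent correlations of 0.3-0.85, the assumed grade distributions, 255 per arm in DB1 and an assumed 217 in DB2. No trial conclusion on the co-primaries is affected.

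**What to change.** An optional improvement. In SAP 8.2.7, before unblinding, state that the between-arm p-value at 2, 4 and 24 hours in each period comes from a van Elteren (stratified Wilcoxon) test with predose disability grade (0, 1, 2, 3) as the stratum. Within a stratum the predose grade is constant, so ranking the change and ranking the postdose grade give the same result. The endpoint therefore remains change in functional disability. Keep the change-from-baseline table as descriptive.

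The cost is one sentence in the SAP and a few lines of SAS (PROC FREQ, CMH with modified ridit scores) on data already collected. A subject without a predose grade has no change score now either, so none is lost on that account. A stratum with subjects from only one arm contributes nothing, which matters only if a grade is very sparse. The small downside is that the p-value no longer comes from the pooled change-score distribution shown in the table; a footnote can say so. The blinded data review in Protocol 10.1, which already covers whether the planned methods are appropriate, is a natural place to record the choice and to look at the pooled predose spread.

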#### **8.2.8. Headache Pain Freedom Among Subjects with Cutaneous Allodynia**

The proportion of subjects who are pain-free at 2 and 4 hours postdose during each DB treatment period among those subjects reporting cutaneous allodynia prior to dosing will be summarized by treatment group and time point for the FAS1 and FAS2. The corresponding p-values from Fisher's exact test will be computed for the comparison between treatment groups.

#### **8.2.9. Headache Pain Freedom Among BMI Categories**

The proportion of subjects who are pain-free at 2 and 4 hours postdose whose BMI is < 30 vs. subjects whose BMI is  $\geq$  30 during each DB treatment period will be summarized by treatment group and time point for the FAS1 and FAS2. The corresponding p-values from Fisher's exact test will be computed for the comparison between treatment groups. The same summary will be conducted for subjects whose BMI is < 25 vs. subjects whose BMI is  $\geq$  25.

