#### **10.7 Determination of Sample Size**

Approximately 600 subjects will be randomized for the DB1 period. Subjects who discontinue participation without completing the study protocol will not be replaced.

The first co-primary endpoint is the comparison of the proportion of subjects who are pain-free at 2 hours after the first dose of study drug. It is assumed that 17.6% of placebo and 29.2% of DFN-15 (treated) subjects will be pain-free at 2 hours. A sample size of 600 subjects will provide 88% power to detect this assumed difference between placebo and DFN-15 at a 5% (2-sided) level of significance and with a 15% dropout rate.

The second co-primary endpoint is the comparison of the proportion of subjects who are free from their Screening MBS among nausea, photophobia, and phonophobia at 2 hours after the first dose of study drug. It is assumed that 28.2% of placebo and 44.7% of DFN-15 (treated) subjects will be free from their Screening MBS at 2 hours. A sample size of 480 subjects will provide 94% power to detect this assumed difference between placebo and DFN-15 at a 5% (2-sided) level of significance and with a 15% dropout rate.

Since the sample size for the first co-primary endpoint is larger than that of the second co-primary endpoint, the larger sample size will be used for the study.

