## 6. GENERAL ASPECTS FOR STATISTICAL ANALYSIS

### 6.1. GENERAL METHODS

#### 6.1.1. Summary Statistics

In general, descriptive statistical methods will be used to summarize the data from this study. With appropriate sample sizes, hypothesis testing can be performed for the co-primary and secondary efficacy endpoints.

The term “treatment group” refers to the applied treatment regimen during DB1 or DB2 (DFN-15 120 mg or placebo). All data collected during the study will be included in subject data listings. All subjects entered into the database will be included in subject data listings. Unless otherwise noted, the data will be sorted first by treatment group, subject number, and then by date within each subject number.

Unless stated otherwise, the term “descriptive statistics” refers to number of subjects (n), mean, median, standard deviation, minimum, and maximum for continuous data and frequencies and percentages for categorical data.

All categorical/qualitative data will be presented using absolute frequency counts and percentages. The total number of subjects in the treatment group overall (N) in the specified population will be used as the denominator for percentage calculations, unless stated otherwise in the table shell. All percentages will be presented in parentheses with 1 decimal point, unless otherwise specified. Percentages equal to 100 will be presented as 100% and percentages will not be presented for zero frequencies.

Unless specified otherwise, all statistical testing and confidence intervals (CIs) will be 2-sided and will be performed using a significance (alpha) level of 0.05.

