### 8.4. SUBGROUP ANALYSES

Exploratory subgroup analyses on the co-primary endpoints will be conducted using the following baseline categories for the FAS1:

- Age (18-34 years, 35-49 years, 50-64 and >=65 years)
- Gender (male and female)
- Ethnicity (Hispanic and non-Hispanic)

For each subgroup, the odds ratio for response and the 95% CI for the odds ratio for each of the co-primary endpoints will be calculated using the treatment group, the subgroup variable, and the treatment-by-subgroup interaction term as covariates in the logistic regression model. Since the results of these subgroup analyses are exploratory, future studies can examine the treatment effect among the subgroup covariates that have a significant treatment-by-subgroup interaction term.

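### The BMI secondary endpoint is worded as a contrast between BMI groups, but the SAP tests only DFN-15 against placebo and plans no estimate or test comparing the BMI categories

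*SAP*

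**What the plan says.** The endpoint, in Protocol 10.4.2, concerns subjects "pain-free at 2 and 4 hours postdose whose BMI is < 30 vs. subjects whose BMI is ≥ 30", with a second contrast at a cut-point of 25, in each double-blind period. SAP 4.2 repeats it. In both lists it is the only secondary endpoint that lacks a clause saying that DFN-15 is compared with placebo. Its only stated contrast is one BMI group against the other.

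SAP 8.2.9 summarizes the pain-free proportions by BMI category, treatment group and time point for FAS1 and FAS2. On testing it says: "The corresponding p-values from Fisher's exact test will be computed for the comparison between treatment groups". SAP 6.1.1 explains that the term treatment group "refers to the applied treatment regimen during DB1 or DB2 (DFN-15 120 mg or placebo". The same section makes tests "2-sided and will be performed using a significance (alpha) level of 0.05" unless stated otherwise.

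SAP 8.4 has a model that can compare subgroups. It uses treatment, the subgroup variable and "the treatment-by-subgroup interaction term as covariates in the logistic regression model". It covers only the co-primary endpoints and only age, gender and ethnicity. SAP 6.6 allows further subgroup analyses but describes them as data driven. Protocol 10.5.2 leaves the analysis of secondary endpoints to the SAP.

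**The concern.** The test in 8.2.9 asks whether DFN-15 beats placebo. The endpoint, as worded, sets one BMI group against another. Nothing in the plan gives a difference, odds ratio, interaction or confidence interval across BMI categories.

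The report would then show two drug-versus-placebo p-values side by side under a heading that contrasts BMI groups. The easy reading is that the drug works in the category with the small p-value and not in the other. That does not follow. Each category holds only part of the sample, so each test has much less power than the trial as a whole, and one significant result beside one non-significant result is common even when the effect is the same in both. At stake is a secondary statement about BMI, which could be left unsupported or be drawn wrongly.

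**Working it through.** **Inputs.** Protocol 10.7: "It is assumed that 17.6% of placebo and 29.2% of DFN-15 (treated) subjects will be pain-free at 2 hours", 600 randomized, 15% dropout. Allocation is 1:1 and alpha is 0.05 two-sided. Evaluable per arm: 600 × 0.85 / 2 = 255. The documents do not give the BMI split, so it is assumed and ranged.

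**Step 1: reproduce the plan's own figure.** Protocol 10.7 states: "A sample size of 600 subjects will provide 88% power to detect this assumed difference between placebo and DFN-15". With the pooled normal approximation, the mean rate is (0.176 + 0.292)/2 = 0.234, and

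z = [0.116 × √255 − 1.96 × √(2 × 0.234 × 0.766)] / √(0.176 × 0.824 + 0.292 × 0.708) = (1.852 − 1.174) / 0.593 = 1.14,

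which gives power 87.4%, close to the stated 88%. Exact power of the planned two-sided Fisher test at 255 per arm is 85.5%. The inputs are therefore read as the plan intends.

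**Step 2: two within-category tests, same true effect in both.** Let A and B be the exact Fisher power in the two BMI categories. The categories are independent, so

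P(exactly one significant) = A(1 − B) + B(1 − A).

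| Assumed BMI split | Per arm in each category | A | B | Exactly one significant |
|---|---|---|---|---|
| 50/50 | 128 and 127 | 0.540 | 0.536 | 49.7% |
| 60/40 | 153 and 102 | 0.626 | 0.438 | 51.6% |
| 30/70 | 76 and 179 | 0.327 | 0.700 | 56.9% |
| 20/80 | 51 and 204 | 0.217 | 0.760 | 64.7% |

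At 50/50, for example: 0.540 × 0.464 + 0.536 × 0.460 = 0.497. Both tests are significant in 0.540 × 0.536 = 28.9% of trials.

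**Step 3: no drug effect in either category (17.6% in both arms).** At 50/50 the rejection rates are 0.034 and 0.034, so exactly one is significant in 6.6% of trials. At 30/70 the figure is 6.4%. Discordance is common only when the drug works.

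**Step 4: a direct comparison.** A Wald test was simulated on the difference between the two log odds ratios (200,000 runs). With equal effects it rejected in 4.4% to 4.8% of runs for splits of 20/80, 30/70, 50/50 and 70/30. Its power at 50/50 is about 31% if the drug works as assumed in one category and not at all in the other.

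**Scope.** The calculation is for DB1 at 2 hours. The plan repeats the analysis at 2 cut-points, 2 time points and 2 periods, so 2 × 2 × 2 = 8 pairs of tests. The SAP 8.2 exclusions (early rescue; mild or no predose pain in DB1) could make the categories smaller than assumed here.

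**The case against.** The strongest reply is that the endpoint states no hypothesis. The title of 8.2.9 parallels that of 8.2.8 on allodynia, and the aim may simply be to show the drug effect in each BMI stratum. Drug-versus-placebo Fisher tests do that, and the tabulated proportions let a reader compare categories by eye. This stands in part. The target is ambiguous, and the endpoint is not wholly without analysis. What is missing is a formal contrast with its uncertainty. The ambiguity is itself a reason for the SAP to name the target.

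A reader might infer that the plan carries a 50% false-positive rate for BMI. The documents do not support that. Section 8.2.9 has no rule that turns discordant p-values into a BMI difference. The 50% is the frequency of discordance, and it becomes an error only if someone later draws that inference.

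A reader might also take it as stated that the Fisher tests are run within each BMI category. That is the natural reading of 8.2.9, but the text does not say so. On any reading, BMI groups are not tested against each other.

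Nor does the point extend to allodynia. That endpoint is worded as DFN-15 against placebo among subjects reporting allodynia predose, and 8.2.8 tests exactly that.

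Finally, trial success under SAP 8.1.1 rests on the co-primary endpoints alone. That is correct, and it limits the weight of the point.

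**Conclusion.** The mismatch is real: the BMI endpoint is worded as a between-category contrast, and the SAP plans descriptive proportions and drug-versus-placebo tests, with no estimate or test across categories. Contrasting the two p-values is not a substitute. With an identical effect in both categories, exactly one would be significant in about 50% to 65% of trials over the splits tried, against under 5% for a direct interaction test. That range rests on three assumptions: the drug works as the sample size section assumes, 255 subjects per arm are evaluable, and the BMI split lies between 50/50 and 20/80 in either direction. With no drug effect the figure is about 6.5%. The point concerns one secondary endpoint and leaves the co-primary conclusion untouched.

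**What to change.** In SAP 8.2.9:

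- State whether the target is BMI as a predictor of pain freedom or BMI as a modifier of the drug effect. These are different questions with different estimates.
- For each cut-point, fit the existing 8.4 logistic model (treatment, BMI category, treatment-by-BMI interaction) to pain freedom at 2 and 4 hours in each double-blind period.
- Report the DFN-15 versus placebo odds ratio with 95% CI in each BMI category, and the interaction estimate with 95% CI. If BMI as a predictor is the target, report the BMI odds ratio with 95% CI as well, and say whether it applies within each arm or averages over both.
- The Fisher p-values may stay as description, with a sentence saying that they are not to be used to infer a BMI difference.

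The cost is one more variable in a model already specified. SAP 7.2 already derives BMI, so no new data are needed. The drawback is the low power of the interaction test (about 31% in the case shown), so a non-significant interaction must not be read as proof of equal effects. The write-up should rest on the estimate and its interval. The allodynia analysis needs no change.
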